Official Study Title	Effects of Transcranial Electrical Stimulation on Task Performance in Healthy Adults
ClinicalTrials.gov Identifier (NCT)	NCT06995560
Study Sponsor	Massachusetts General Hospital
Principal Investigator	[name]
Affiliation	Massachusetts General Hospital / Harvard Medical School
Study Type	Interventional Study
Intervention	Transcranial Electrical Stimulation (tES)
Primary Outcomes	ROBoT-r Task Performance (During and Post-Stimulation)
Secondary Outcomes	tES Adverse Effects Questionnaire; fNIRS Hemodynamic Activation (HbD)
Document Type	Study Protocol
Protocol Date	April 4, 2024

Protocol Title: Preliminary investigations of transcranial electrical stimulation effects on neurophysiology and behavior

Principal/Overall Investigator: [name]

Description of Subject Population: Healthy, adult volunteers, age 18-64

I. BACKGROUND AND SIGNIFICANCE

Transcranial electrical stimulation (tES) is a technology that can be made small, lightweight, and non-invasive for deployment in a wide variety of domains. Following hundreds of studies, tES has been shown to improve learning, memory, attention and other cognitive capabilities in healthy subjects, as well as providing benefits in psychiatric and neurological patient populations. However, despite these findings, there remain a large number of unknowns about tES. A better understanding of the effects of tES has the potential for wide-ranging benefits in performance maintenance/enhancement and potentially even therapeutic treatments.

More specifically, the studies conducted over the past decade suggest that low-intensity (e.g., <2mA) transcranial electrical stimulation (tES) can influence behavioral performance on a wide range of tasks. However, there remains uncertainty regarding (1) the significant inter-individual variability in response to brain stimulation, (2) variability in neurophysiological effects regarding brain activity and inter-regional connectivity, (3) the magnitude, nature and duration of immediate- vs. after-effects of stimulation, (4) the role of task-type in response to stimulation, and even (5) the underlying mechanism(s) of the tES effects¹. Regarding tasks, one domain that has seen particularly limited investigation is the performance of complex tasks that require multiple cognitive capabilities to be used simultaneously. There are numerous examples, but tasks like robotic/teleoperation, navigation, etc. are all relevant. It is unknown what effect tES may have on such tasks, which can be highly relevant for operational settings. **This IRB protocol is designed to support multiple substudies to address the above research questions.**

II. SPECIFIC AIMS

- 1) Characterize the relationship between the type, location and intensity of stimulation on *behavioral responses*.
- 2) Characterize the relationship between the type, location and intensity of stimulation on regional *neurophysiological responses*.
- 3) Characterize the relationship between the type, location and intensity of stimulation on the *after-effects on performance*.

III. SUBJECT SELECTION

Initial substudies will be conducted on healthy volunteers. Later substudies will be conducted on select patient populations (added via protocol amendment).

Healthy volunteers

We will recruit healthy individuals, age 18-64. In some substudies, we will restrict this further to the age range of 25-55 as representative of the astronaut population, given our group's focus on spaceflight-relevant research.

Inclusion criteria:

- Aged 18-64 years.
- No history of head injury or other neurological or psychiatric disorders, particularly bipolar disorder ².
- No history of cardiac disease, including ischemic heart disease, arrhythmia, hypertension, or syncope.
- No metal implants in the head
- No implanted electronic devices.
- Not taking any drugs known to effect neural or cardiovascular function.
- Ability to give a written and dated informed consent.

Exclusion criteria:

- Smoking within the last year
- Current illegal drug use
- Alcohol abuse
- Pregnancy, as determined by urine pregnancy screening test
- Participation in another brain stimulation protocol within the past month.

IV. SUBJECT ENROLLMENT

The series of studies is projected to start in October 2020 and to end in December, 2025. During this period, we plan to enroll a total of 120 volunteers. This will allow us to conduct a series of preliminary investigations (typically n=20-30) to address the protocol's specific aims as well as to help develop hypotheses for future research.

a. Methods of enrollment, including procedures for patient registration and/or randomization:

Healthy control volunteers will be recruited through postings within the hospital environment, via email bulletin boards, and through engagement with the Rally with Partners program. Additionally, recruitment will extend to individuals who have previously expressed interest in participating in research studies led by the Principal Investigator (PI).

The recruitment procedure will include the integration of a REDCap survey as a preliminary screening tool to assess potential participants' eligibility for study inclusion. Prospective participants will have access to the REDCap survey through various channels, including direct QR code links provided on advertisements and survey links on the Rally page.

Upon accessing the REDCap survey, individuals will be presented with a study description and a link to the Rally webpage for detailed information and direct contact with study staff. Completion of the REDCap survey will serve as an initial step in the recruitment process. However, individuals expressing interest via the Rally page can opt for phone calls for initial screening. If this is preferred, a direct phone call will be made to the subject. Contact information for direct communication with study staff will be provided to individuals expressing interest in participating, regardless of completing the REDCap survey, to accommodate a preference for direct contact. Following completion of the initial screening, participants who meet the initial eligibility criteria will be contacted via telephone.

b. Procedures for obtaining informed consent (including timing of consent process):

This follow-up will involve more detailed questions to determine suitability for study enrollment, clarifying responses provided during initial screening, and answering any remaining questions they may have about the study. If the individual passes all eligibility criteria and is interested in participating, they will be provided with a copy of the consent form in advance and scheduled for study participation. Upon arrival, volunteers will be brought to the research exam room, where one of the investigators will explain the study in detail. In addition, the volunteer will be introduced to the behavioral tasks, the brain stimulation equipment, and the monitoring equipment to be used. Volunteers will be asked if they have questions about the study and express any concerns. They will also be informed of their right to withdraw from the study at any time. If they choose to participate, we will obtain their written informed consent, which will be countersigned by one of the study investigators.

c. Treatment assignment, and randomization (if applicable):

The study does not involve treatment assignment and/or medications, and each subject undergoing tES will have both active and sham conditions (i.e., they will serve as their own control). Therefore, treatment assignment and randomization is not applicable.

V. STUDY PROCEDURES

All investigations will involve computerized versions of standardized cognitive tests (e.g., N-back, continuous performance task, reaction time tasks, decision making tasks, spatial cognition, etc.) and/or more complex/operational performance tasks (e.g., robotic teleoperation, driving/navigation, or other computerized task).

Every study will involve two phases: (1) familiarization/training, (2) testing with/without brain stimulation. To address our aims regarding after-effects, some substudies will involve a third phase (3) post-testing without any additional brain stimulation. These phases will be described separately.

Phase 1 – Familiarization/Training: Tasks will be computerized tests that range from approximately 2-60 min in length. These will assess memory, attention, risk tolerance, executive function, and various other cognitive processes, sometimes in combination. For familiarization, subjects will have the computerized tasks explained to them, and then they will practice the tasks. Such familiarization/training sessions will take roughly 5-120 minutes, depending on the

duration and complexity of the task. This phase may be split across separate visits based on scheduling constraints or extent of task training required. Physiological monitoring (see Phase 2) will be conducted during familiarization task performance as well, to help adapt subject to the related sensors. Finally, subjects will be familiarized with the tES device, setup, and “feel”. This will involve full rigging and then experiencing a “sham” stimulation condition which includes the ramp-up, less than 30 sec of stimulation, and ramp-down—a condition which generally feels identical to an active stimulation condition.

Phase 2 – Testing: Once familiarization and training is complete, the second phase will involve up to 5 sessions of tES brain stimulation, conducted on 1-5 separate visits (also dependent on the duration of the behavioral tasks and scheduling constraints). Each Testing session will proceed as follows:

Physiological Monitoring Setup: If applicable, subjects will first be rigged for physiological recording, including one or more of the following: near-infrared spectroscopy for brain function monitoring, EEG for cerebral electrophysiological monitoring, EMG for muscle monitoring (thumb, arm, and/or cheek), EOG for eye movement monitoring (to detect artifacts in EEG), ECG for heart rate and variability monitoring, respiration, skin temperature, accelerometry and blood pressure. Our group’s NINscan-SE device can record all of these simultaneously, using superficial skin sensors which will be coupled to the skin via standard stick-on gel electrodes, or comfortable fabric straps. These will be secured so as not to contact or interfere with the placement of any of the tES electrodes.

tES setup: We will use a Soterix Medical HD-MxN-33 fully programmable system for double-blind stimulation protocols (Soterix Medical, New York, NY) with electrodes attached to custom high-definition plastic holders, filled with saline-soaked sponges or conductive electrolyte gel designed for tES, all embedded in the head cap. Electrode placement will be guided by current-flow modeling using HD-Explore and HD-Targets (Soterix Medical, New York, NY), with sites selected based on prior tES research for that particular type of task (when possible), or other neuroimaging study (e.g., fMRI, fNIRS) that indicates the approximate location of networks involved in the behavioral tasks to be tested. Stimulation intensity (peak to peak) will be set below 2.0 mA (and below 1.0 mA for montages near the temporal bone window). Stimulation will be conducted during the task(s), for no more than 45 min continuously, and for a maximum of 60 min total per day. For tACS at two locations, we will use either in-phase or anti-phase stimulation to enhance or suppress (respectively) brain synchronization and/or connectivity between the two regions³⁻⁶.

tES protocol: Our studies will all be double-blind sham controlled. The exact stimulation protocol will depend slightly on the specific aim we are addressing. However, the stimulation parameters will be restricted to the following:

- *Stimulation type:* direct current (tDCS), alternating current (tACS), or random noise stimulation (tRNS)
- *Stimulation intensity:* range=0.4-2.0 mA; this will generally be ~1.5 mA based on current modeling, but with a maximum of 2.0mA peak current (and a maximum of 1.0 mA for electrodes in the vicinity of the temporal bone window). All stimulations will begin with a 20-sec ramp-up and end with a 20-sec ramp-down period to minimize tingling and itching.

- *Stimulation frequency*: range=1-200Hz for tACS and tRNS only; based on prior findings of tACS enhancement of endogenous oscillations we will use tACS in the 1-40Hz range, and based on prior tRNS findings of performance enhancement on sensory and motor tasks with 100-200Hz oscillations of random amplitudes, tRNS will focus on the 100-200Hz range.
- *Stimulation duration*: range=5-45 min for a single continuous stimulation, with a maximum per day limit of 60 min (i.e., remaining within the low-intensity tES regime ²)
- *Stimulation session repetitions*: range=1-5 (again, remaining within the 60 min/day total stimulation limit); hence a maximum of 5 days of stimulation
- *Stimulation locations*: range=1-3; each subject will undergo tES over 1-3 different brain regions, but no more than 2 brain regions will be stimulated at the same time, always limited as described above.

Each subject will perform the task(s) from their familiarization/training session with stimulation, as well as without stimulation (sham) as part of Phase 2. We will counterbalance orders within/between subjects. A second stimulation period may be repeated on a given stimulation day, within the limits described above. The sham stimulation condition will follow the same procedure as the active condition, but stimulation will last only 30 seconds, ramping up and down at the beginning and end of the period to simulate the tingling sensation that subjects typically experience and then quickly habituate to during active stimulation ⁷.

Following each session, a safety questionnaire ⁸ will be administered, including questions regarding attention, concentration, mood, vision, headache, fatigue, and skin sensations under the stimulating electrodes.

Phase 3 - Post-testing: For studies investigating after-effects of stimulation, participants will perform the task(s) with physiological monitoring again without stimulation at up to 6 time points during the following week. Any interval >10 hours will be conducted during a separate visit the following day.

Overall Limits: Again, regardless of stimulation condition (stimulation or task duration, repetitions, or number of brain locations stimulated), no subject will exceed 2.0 mA peak-to-peak, 45 min in a single stimulation session or 60 min/day.

Substudy 1: For this study, our primary outcome will be a 30 min computerized track-and-capture task battery involving dual-hand controllers. Phase 1 will last ~3 hours for consent, familiarization and task training. In Phase 2, subjects will undergo 45 min stimulation (or sham), perform the task battery, another 45 min of sham (or stim) one week later, and again perform the task battery. Stimulation will involve tDCS over the target location with a net intensity of 1.5-1.9mA depending on target and electrode configuration. Sham will involve the same electrode placements and the same 20-sec current ramp-up followed immediately by the 20-sec ramp-down. This generates sensory experiences similar to actual stimulation but without brain stimulation effects. Throughout Phase 2 we will record near-infrared spectroscopy (NIRS) over the prefrontal cortex, as well as 2-channel EEG (F3/F4), 1-channel ECG, 1-channel EMG, respiration, blood pressure, accelerometry and skin temperature. For Phase 3, subjects will be asked to return on two consecutive days after each stimulation to repeat the task battery and physiological monitoring (no brain stimulation on follow up days). This will result in a total of 7 visits over 11 days (Phase 1=~3 hours on day 1, Phase 2=~3 hours on day 2 and day 9, Phase

3~1 hour on each of days 3, 4, 10 and 11). For this substudy, N=20 subjects will be stimulated over the left dorsolateral prefrontal cortex (DLPFC), and a separate N=20 subjects will undergo stimulation over the left insular cortex. Electrode configurations for each location will be based on current source modeling with Soterix Medical's HD-Targets modeling software.

VI. BIOSTATISTICAL ANALYSIS

The specific metrics and our methods to calculate them appear below. All metrics will be cross-checked and verified prior to analysis. NINscan-derived measures will be processed programmatically to identify signal quality or dropout issues, any of which will be manually cross-checked, all per our prior work.

Preprocessing:

Performance Data: Behavioral task data will be evaluated per standard methods, typically summarizing accuracy and response time (e.g., ¹⁰) or summarizing various other continuous performance metrics such as smoothness of performance (e.g. ¹¹). This will provide a range of measures of individual cognitive capacities as well as operationally relevant performance metrics for both sham and stimulation conditions.

NIRS: We will use the modified Beer-Lambert law to compute concentrations of oxy-, deoxy- and total-hemoglobin ([O₂Hb], [HHb], and [HbT] respectively). Close-detectors measuring scalp-only signals will be used as regressors to filter out systemic effects in most cases. The resulting data will be used to compute task-related functional activation, resting cardiac and vasomotor pulsatility, and inter-hemispheric functional connectivity at resting baseline, all per prior work ¹²⁻¹⁵.

Systemic Physiology: For ECG, we will compute average heart rate and heart rate variability via peak-detection algorithms. Respiratory rate and volume can be computed from the respiratory sensor. The accelerometer will be fed through a standard actigraphy algorithm ¹⁶. EEG will be examined through power spectral analysis after band-filtering to the frequencies of interest (e.g., 0.1-40 Hz).

Analysis:

We will first use descriptive statistics (means, standard deviations, skew, kurtosis) to characterize each metric within each subject and condition. Given the known speed-accuracy trade-off, we will make response time and accuracy the primary measures for each task (other metrics being secondary). We will then quantify the relationships between behavioral responses (Aim 1), neurophysiological responses (Aim 2) and after-effects on behavioral performance (Aim 3) as a function of type, location, intensity, and duration of brain stimulation. This will be conducted via mixed effects linear modelling approaches, with appropriate follow-up testing, including linearity, calibration, additivity, outliers, and post-hoc analyses to help identify nonlinearities such as onset of effects as a function of stimulation duration or intensity, and so forth.

We will report all p-values as uncorrected but include the number of statistical tests performed.

VII. RISKS AND DISCOMFORTS

Near Infrared Spectroscopy: NIRS monitoring requires coupling optodes to the skin on the scalp. This is achieved by fastening the optodes to a stretchy cap or strap, and positioning that over the target portion of the head. The subject's hair may need to be parted in the location of the optodes to provide better coupling to the skin. The procedure does not cause pain or distress, although extended wearing of the device may lead to discomfort due to the mild pressure. The instrument will be made as insensitive as possible to head motion, and hence there are essentially no restrictions on head motion. Near Infrared Spectroscopy (NIRS) is an investigational tool and although no adverse effects have been reported, it is possible that effects not yet reported may occur. The NIRS devices use low power laser diodes emitting light at 780 and 830 nm. As such, there are general risks associated with laser use including over-exposure of the skin or eyes. The optical power delivered to the skin of the subject is $P \sim 12\text{mW}$. Since this power is distributed over an area of 3 mm or more, $A = \pi(0.3/2)^2 \text{ cm}^2$, the optical fluence at the skin is $P/A \sim 0.17\text{W/cm}^2$. This value is smaller than the maximum permissible exposure (MPE) for skin exposure to a laser beam, as indicated by the American National Standards Institute (see the ANSI Standard Z136.1, Table I). The MPE indicated by the American National Standards Institute (ANSI) standards for skin exposure ranges from 0.2W/cm^2 at 690 nm to 0.4W/cm^2 at 850nm. Moreover, the CW-NIRS laser light is not collimated and diverges in a wide angle (>50 deg) at the probe end because of an optical diffuser attached to the laser output window. This would result in a Nominal Ocular Hazard Distance (NOHD) of less than 5 cm, which is lower than the 10 cm focusing distance of the retina. Hence, the NIRS devices connected to the probes do not necessitate eye protection.

Transcranial electrical stimulation: It is expected that a minority of subjects will experience tingling and/or itching beneath the electrodes during stimulation, or potentially post-stimulation fatigue, mild headache, or local discomfort. Less commonly, subjects may experience nausea and in rare cases subjects have been reported to experience insomnia. In very rare cases, skin burns could be experienced due to inappropriate direct contact of electrodes with the skin.

EEG/EMG/ECG/EOG/respiration monitoring requires coupling a sensor to the skin via electrodes. This can cause skin irritation.

Behavioral testing: There are no risks associated with the behavioral testing aside from the possibility of fatigue or boredom. Time periods between data collection will be subject-controlled in an attempt to reduce both.

VIII. POTENTIAL BENEFITS

There are no direct benefits to the participants in this study. The investigators hope that successful completion of this series of substudies will provide a significantly improved, systematic understanding of the relationship between tES parameters (location, intensity, and type of stimulation) and (i) neurophysiological brain responses, and (ii) behavioral effects, both immediate and over time.

IX. MONITORING AND QUALITY ASSURANCE

The integrity of tES electrodes must be checked every session and the electrode impedance needs to be continuously monitored to ensure adequate electrical coupling with the skin. All tES stimulation protocols will be double-checked by a second experimenter prior to implementation to ensure they comply with protocol limits described above. Given the low light powers involved in near-infrared spectroscopy, the NIRS system is considered a non-significant risk device.

X. REFERENCES

5. Reinhart RMG. Disruption and rescue of interareal theta phase coupling and adaptive behavior. *Proc Natl Acad Sci U S A*. 2017;114(43):11542-11547.

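### Section IV.c calls randomisation not applicable because subjects are their own controls, yet active/sham order is an assignment and no random or concealed method of making it is described

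*Combined protocol and SAP*

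**What the plan says.** Section IV.c states that the study involves no treatment assignment, that each subject has both conditions and so acts as their own control, and concludes: "Therefore, treatment assignment and randomization is not applicable".

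Section V (tES protocol) says: "We will counterbalance orders within/between subjects". It gives no ratio, list, method or responsible person. The same section states "Our studies will all be double-blind sham controlled" and names a stimulator described as a "fully programmable system for double-blind stimulation protocols".

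Section V (Substudy 1) leaves the order open for each subject: "subjects will undergo 45 min stimulation (or sham), perform the task battery, another 45 min of sham (or stim) one week later". The task is trained: "Phase 1 will last ~3 hours for consent, familiarization and task training". The battery is then repeated on the two days after each stimulation visit, so practice on days 3 and 4 falls between the two stimulation visits on days 2 and 9. There are 20 subjects for each of two stimulation targets.

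Section VI specifies linear mixed models and names no period or sequence term. Section IX adds a safeguard: "All tES stimulation protocols will be double-checked by a second experimenter prior to implementation". Its stated purpose is compliance with the protocol's stimulation limits.

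**The concern.** Serving as one's own control cancels stable differences in skill. It does not cancel change between the first and second session, and on a trained, repeated task such change is plausible. Someone must decide which subjects get active first and which get sham first. That decision is a treatment assignment, and Section V acknowledges it by counterbalancing. Section IV.c therefore conflicts with Section V, and the reason it gives for dispensing with randomisation is not valid.

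Counterbalancing controls how many subjects follow each order. It does not control which subjects do. If faster learners tend to be placed in one order, or if the next order can be guessed when a subject is scheduled, the order groups can differ systematically. That difference enters the stimulation effect. A p-value or confidence interval allows for chance differences between the groups, not for systematic ones.

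**Working it through.** The protocol states no alpha, power, effect size or SD, so there is no figure of its own to reproduce. What follows is illustrative.

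**Inputs.** From Section V, Substudy 1: two periods and N=20 per target. Assumed: two-sided 0.05, 80% power, no carry-over, a 10:10 split, and learning-gain gaps of 0.2, 0.4 and 0.6. All effects are in units of the SD of the paired difference (active minus sham).

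**Bias formula.** Let τ be the true effect, and let g_A and g_S be the mean gains from session 1 to session 2 in the active-first and sham-first groups.
- Active-first: expected difference = τ − g_A.
- Sham-first: expected difference = τ + g_S.
- Average of the two: τ + (g_S − g_A)/2.

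If g_A = g_S, the bias is zero. A balanced split therefore removes a common learning trend, whether or not the order was drawn at random. If the gains differ systematically, half the gap remains. A period term does not remove it, because that term fits one common gain.

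**Detectable effect.** A paired t-test with n=20 under the assumed alpha and power detects 0.660 SD.

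**Size of the bias and false-positive rate.** With a period-adjusted test at 10:10, the standard error is 1/√20 = 0.224 on 18 degrees of freedom. With no true effect:

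| Assumed gap | Bias = gap/2 | Bias/SE | False-positive rate | Bias/0.66 |
|---|---|---|---|---|
| 0.2 | 0.10 | 0.45 | 7% | 15% |
| 0.4 | 0.20 | 0.89 | 14% | 30% |
| 0.6 | 0.30 | 1.34 | 25% | 45% |

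**The unit matters.** If the 0.6 gap is instead in single-session within-subject SDs with independent errors, the bias is 0.30/√2 = 0.21 SD of the paired difference, and 0.21/0.66 = 32%.

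**Why the model should carry period.** With a 10:10 split and a common period effect of 0.5 SD (assumed), the unadjusted paired test has no bias, but its type I error is about 0.028 instead of 0.05. The period effect inflates the estimated variance, so the test loses sensitivity.

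**The case against.** The strongest reply is that the main learning threat is already dealt with: a counterbalanced 10:10 split gives zero bias from a common practice effect. That stands. What remains is selection or predictability, and the protocol contains no evidence of either.

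A reader might infer that staff choose the order openly, or that it is unconcealed. The documents do not support this. They do not describe the mechanism, they state double-blinding for all studies, and they name equipment suited to it. Condition blinding is not the same as concealing the order, but silence about concealment does not show that it is absent.

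A reader might also infer that the Section IX check unmasks the people running sessions. That is not shown either. The section does not say that the check displays the condition, or that the checker runs or scores the session.

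The gap sizes are assumptions. With 10 subjects per order, proper randomisation would itself produce a gap of 0.6 or more in either direction about 18% of the time (paired-difference SD units). This is correct, but such a gap would be chance, which the standard error covers. A systematic gap is not covered.

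Uneven splits such as 13:7 bias an analysis without a period term by 0.30 times the period effect. That is a problem of imbalance, not of missing randomisation: simple randomisation gives 14:6 or worse with probability 0.115. It is an argument for blocking and a period term, and it does not enlarge this point.

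Finally, the series is described as preliminary and hypothesis-developing. That lowers the severity but does not make the reasoning in Section IV.c sound.

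**Conclusion.** The point holds in a limited form. Section IV.c states a rule, not merely an omission, and the rule rests on an invalid reason and conflicts with Section V. Following it permits non-random allocation to order, which neither an even split nor a period term corrects. The protocol describes no random method, and it is silent on who holds the order and whether the Section IX check shows the condition.

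The bias is half of any systematic difference in learning gain: 0.1 to 0.3 SD of the paired difference for assumed gaps of 0.2 to 0.6, against a detectable effect of about 0.66 SD. These figures rest on the assumed gaps, alpha and power, a 10:10 split and no carry-over. They show what could happen, not what has happened. Should-fix.

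**What to change.** 1. Replace the Section IV.c conclusion with: *Sequence (active-first / sham-first) will be randomised 1:1 from a computer-generated list in permuted blocks of varying size, separately within each stimulation target.*
2. Have an existing team member who does not run or score those sessions hold the list and load coded programmes into the stimulator.
3. Have the Section IX limits check done on the coded programme by someone not running that session.
4. In Section V, change the counterbalancing sentence to specify a randomised, balanced order.
5. In Section VI, include period in the mixed model.
6. Section IV projects a start in October 2020 and the protocol is dated April 2024, so sessions may already have been run. For any that have, document how order was actually set.

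The cost is a short amendment, a generated list and minor separation of tasks within the existing team. The protocol gives no staffing numbers, so the team should confirm that the separation is workable. No added visits or participants are needed.

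### In Substudy 1 the adverse-effects questionnaire is scheduled only on the two session days, so insomnia, a named risk, has no form at the four follow-up visits where it could be reported

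*Combined protocol and SAP*

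**What the plan says.** The cover table lists the "tES Adverse Effects Questionnaire" as a secondary outcome.

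Its only scheduling statement is in Section V, under Phase 2: "Following each session, a safety questionnaire ⁸ will be administered". The opening of Phase 2 shows what a session is: "the second phase will involve up to 5 sessions of tES brain stimulation, conducted on 1-5 separate visits". The form is described as including "questions regarding attention, concentration, mood, vision, headache, fatigue, and skin sensations under the stimulating electrodes".

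Phase 3 follows as a separate paragraph and mentions only task performance with physiological recording. The Substudy 1 text agrees: "subjects will be asked to return on two consecutive days after each stimulation to repeat the task battery and physiological monitoring". Neither mentions a questionnaire.

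Section VII names among the stimulation risks "potentially post-stimulation fatigue, mild headache, or local discomfort", and adds that "subjects may experience nausea and in rare cases subjects have been reported to experience insomnia". It gives no rates. Section IX covers electrode integrity, impedance and a second check of the stimulation settings, and describes no other collection of adverse effects.

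**The concern.** Insomnia caused by a session can be reported only after a night has passed. A form completed on the session day cannot record it, whatever items the form contains. Participants in Substudy 1 are back on site on each of the next two days, yet no form is planned then. The same applies to any symptom that begins or persists after the participant has gone home.

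Two things are at stake. First, a secondary outcome on adverse effects would be silent on one of the risks that the protocol names, and an absence of recorded insomnia could be taken as evidence when nobody had asked. Second, Aim 3 concerns after-effects on performance, which Substudy 1 reads from these same follow-up visits. If stimulation disturbed sleep, that would be one route to a next-day change in performance, and the planned data would give no hint of it.

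**Working it through.** **Inputs.** From the Substudy 1 text in Section V: Phase 1 on day 1; Phase 2 on days 2 and 9; Phase 3 on days 3, 4, 10 and 11; 20 subjects stimulated over the left DLPFC and a separate 20 over the left insula. From Phase 2 in Section V: order is counterbalanced. Even counterbalancing is my assumption.

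**Visit count.** 1 + 2 + 4 = 7 visits, spanning days 1 to 11. This reproduces the plan's own figure of 7 visits over 11 days.

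**Forms as planned.** Two per subject (days 2 and 9), so 40 × 2 = 80 in all. Follow-up visits with a form: 0 of 4.

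**Gap after each session.**
- After day 2: next visit on day 3 (1 day later); next form on day 9 (9 − 2 = 7 days later), by which time the other condition has been given.
- After day 9: next visit on day 10 (1 day later); no further form.
- With even counterbalancing, 40 / 2 = 20 active exposures fall on day 9 and have no later form. The other 20 fall on day 2, and their next form follows sham a week later.

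**Forms with the follow-up visits included.** Six per subject, so 40 × 6 = 240. The addition is 240 − 80 = 160. Each subject has two follow-up visits after active and two after sham, so 80 of the 160 follow active and 80 follow sham. No visit is added.

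**What complete capture would support.** With zero events in n exposures, the one-sided exact 95% upper bound solves (1 − p)^n = 0.05, so p = 1 − 0.05^(1/n).
- n = 20 (one montage): 1 − 0.05^(1/20) = 13.9%.
- n = 40 (both montages pooled): 1 − 0.05^(1/40) = 7.2%.

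**Chance of seeing at least one event**, 1 − (1 − p)^n. The documents give no rate, so p is assumed.

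| Assumed rate | n = 20 | n = 40 |
|---|---|---|
| 1% | 18% | 33% |
| 2% | 33% | 55% |
| 5% | 64% | 87% |

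These figures apply only if the night after the session is asked about. Under the written schedule a zero count for overnight effects has no denominator, and no bound follows.

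**The case against.** The strongest case against is that the gap is narrow and the gain modest. The four visits belong to one substudy of a preliminary programme in healthy volunteers, and no primary outcome is affected. Insomnia is described as rare, and at an assumed 1% rate even complete capture in 40 subjects would show an event only about a third of the time. Participants are seen in person at every follow-up visit and could volunteer a complaint. All of this stands, and it limits the weight of the point. It does not remove it: spontaneous reports are not solicited under any described procedure and would not give a systematic record by condition.

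A reader might also infer more than the documents support:

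- **That post-stimulation fatigue and headache are missed.** Both are listed items, as are skin sensations, so what is present at session end is recorded. Section VII does not call any effect delayed, and Section V does not say how soon after a session the form is given.
- **That the form lacks sleep and nausea items.** The list is introduced as partial, and the cited instrument is not available here. Their absence is not established. The timing problem holds either way.
- **That no adverse-effect information reaches the investigators at follow-up.** The text is silent, which is weaker. The consent pages are not in the reviewed text, so nothing can be concluded about instructions given there.
- **That poor sleep would confound the Aim 3 contrast.** If active stimulation worsens sleep and sleep changes performance, sleep is a mediator on the causal path. The total active-versus-sham contrast properly includes it.
- **That a planned safety test is invalidated.** Section VI specifies no comparison for the questionnaire.

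Two possible rescues were considered. A broad reading of session that took in Phase 3 is not supported, because the sentence sits in Phase 2 and sessions there are stimulation sessions. Section VI mentions an actigraphy algorithm, but no overnight or take-home recording is described.

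**Conclusion.** The point holds in a limited form. In Substudy 1 no scheduled form captures insomnia promptly after either session, and none captures it at all after day 9. Later-arising or persisting symptoms are likewise not systematically recorded. This rests on reading the Phase 2 placement together with the silence of Phase 3. The figure of about 20 active exposures rests on even counterbalancing. The upper bounds also assume no dropout, and the pooled one assumes that combining two different montages is acceptable; the per-montage bound is the more cautious statement.

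It is a worthwhile, inexpensive improvement to a listed secondary outcome. It does not threaten the primary analysis. Other substudies may have up to six post-test time points or none, so the visit count should not be carried over to them.

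**What to change.** Give the same questionnaire at the start of each Phase 3 visit, before the tasks, with a recall period running from the last visit. Confirm that the cited instrument asks about sleep and nausea, and add those items if it does not.

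Report the immediate and next-day windows separately and descriptively, by active and sham, with the number of completed forms as the denominator and results by montage. The sleep item may help in interpreting next-day after-effects as a possible mediator; it should not be an adjustment covariate in the Aim 3 model.

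The cost is four short forms per subject, a few minutes each at visits already scheduled, and a minor amendment. It also adds a few descriptive comparisons. Section VI reports p-values uncorrected, so any that are tested should enter the stated count of tests.
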